24. Prisoners, institutionalized individuals or vulnerable population
(The real-world group will not have any exclusion criteria related to timolol (criteria 18-22)

(*)Note: The exclusion criteria were modified compared to the original submission based on the recommendation from the DMC, which suggested that these criteria would significantly impair the enrollment. Those were also revised upon evaluation by the consultant Cardiologist, [name].

TREATMENT: Total duration of study per subject: Up to 31 weeks (Includes to 2 weeks of screening and up to 16 weeks until the end of the follow-up period). 12 weeks for the real-world group.

DURATION OF ADMINISTRATION: Daily application for 12 weeks (starting at Visit 3/Week 3).

STUDY DESIGN: This is a prospective, randomized, double blinded, controlled, and parallel-group study with 2 arms: β AR antagonist (SOC plus topically applied Timoptic-XE®) and control (standard of care (SOC) plus non-biologically active gel (hydrogel, Kendall®, placebo medication)).

EFFICACY ENDPOINTS:**PRIMARY EFFICACY OUTCOME**

1. Complete closure of ulcer by Visit 14/Week 14

SECONDARY EFFICACY OUTCOME

1. Complete closure of ulcer by Week 31
2. Percent difference change in size from the randomization visit to the endpoint visit (post 12 weeks)
3. Time to wound closure
4. Rate of ulcer healing
5. Change in transepidermal water loss of re-epithelialized wound after wound closure

SAFETY ENDPOINT:**PRIMARY SAFETY OUTCOME**

1. Timolol serum levels during the treatment phase

SECONDARY SAFETY OUTCOME

1. Mean changes from baseline in systolic and diastolic blood pressure in mmHg
2. Mean changes from baseline in heart rate in beats per minute
3. Adverse events associated with the use of timolol.

QUALITY OF LIFE ASSESSMENT: We will use ANCOVA to analyze the quality of life from the VR-36 Health Survey and the Lower Extremity Functional Scale Outcome Questionnaire.

DATA ANALYSIS:

The primary outcome is complete ulcer closure by Week 12 (end of the Active Phase) of the study and the rate of ulcer healing by the 12th week of care between the two arms.

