Hypothesis to be tested: The null hypothesis is that there is no difference in the proportion of subjects with complete wound closure of DFU between the timolol treatment group and the control group. Complete wound closure is defined as 100% closure, or skin re-epithelialization without any drainage present or dressing requirements. Two-sided Fisher's exact test will be used to compare the proportion of complete ulcer closure by Week 12 (end of the Active Phase) of the study and the rate of ulcer healing by the 12th week of care between the two arms. The Kaplan-Meier method will be used to estimate the survival function of time to achieve complete ulcer closure (if less than 12 weeks) for each arm, and a two-sided log-rank test will be used to compare the survival curves between the two arms.

The area of the target ulcer will be summarized by treatment group and visit. Both actual value and change from the previous visits ulcer area will be presented. A second summary of target ulcer area will also be given which will present change from baseline. The weekly change and the percentage weekly change in the target ulcer area from visit to visit will be summarized by treatment group and visit. The two-sided t-test or Wilcoxon rank-sum test as appropriate will be used to compare relative ulcer area from baseline to Week 12 between the two arms.

Chi-square test or Fisher's exact test as appropriate will be used to compare wound healing rates in relationship to wound size, as well as wound healing rates between the treatment groups at the 4-week follow-up and at the 12-week follow-up period and recidivism rate.

Additional secondary analyses to evaluate the association of specific wound characteristics (such as wound size, wound location) and subject characteristics (body mass index, chronicity of the wound, history of DVT, length of diabetes, HbA1c, and ABI/toe pressure will be conducted using logistic regression. Further logistic regression will be used to investigate the relationship between the occurrence of each type of adverse event and treatment in order to adjust for each of the potential confounding factors previously listed.

A two-way ANOVA with a post hoc test will be used to determine the relationship between timolol serum levels and wound healing.

Further statistical analysis will be used to determine the relationship between serum inflammatory markers and wound healing.

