4.3.3 Treatment Phase (Visits 4 to 14/Weeks 4 to 14)

Subjects will be evaluated and receive treatments on weekly basis (7 days +/- 2 days).

Appointments will be made as determined by investigator at each VA facility.

- All subjects will have weekly visit including:
 - Vital signs
 - Ulcer assessment and measurement
 - Lab tests per protocol
 - Sharp debridement
 - Weeks 1-9: debrided tissue will be collected and analyzed for molecular markers of inflammatory characterization of wound microbiome.
 - Wound cleansing and moist wound healing dressing
 - Infection assessment if indicated with confirmatory bacterial culture (deep swab curette, tissue specimen/biopsy), radiographical X-rays and blood work (CBC, ESR, CRP, and chemistry) if deemed necessary by investigator clinician.
 - Use of an offloading device that protects the wound from pressure or trauma related to ambulation and other acts of daily living. The total contact cast or instant total contact cast would be ideal offloading devices. However, given the nature and complexities associated with DFU, it is unrealistic to expect that all patients to tolerate such offloading devices. Thus, the offloading device provided will be dependent on the subjects' ability to tolerate the specific offloading device. Adherence to offloading device will be evaluated by the investigator at each visit by observing plantar wear patterns and inquiring from the patient if offloading was used consistently as instructed. Alternative to total contact cast or instant total contact cast (cam walker), offloading devices will be offered including, but not limited to the use of felt/foam adhesive/post op shoe, custom offloading insole, and customized healing shoe in combination with gait assistive device such as a roll-a-bout scooter, walker, wheelchair or motorized scooter.
 - Application of treatments:
 - Standard of Care: Application of non biologically active gel (hydrogel as placebo medication), non-adhesive dressing (Adaptic® or Mepitel®), over wound bed, covered by dry gauze dressings
 - Timoptic-XE®: Application of Timoptic-XE®, non-adhesive dressing (Adaptic® or Mepitel®), over wound bed, covered by dry gauze dressings. Up to 12 weeks of daily applications will be done to wound until healed.
 - Offloading devices (see above)

- Changes in concomitant medications, adverse events, compliance to offloading, will be recorded.

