- If ulcers heal sooner than 12 weeks, the subject will be assessed the following week for a confirmatory visit, followed another week later by a 2nd confirmatory visit. Ulcer healing is defined by 100% epithelialization as determined by the clinician. The subject with healed ulcer will also return for follow-up visits Weeks 19, 23, 27 & 31 (visits 16, 17, 18 and 19).
 - Vapometer recordings will be collected on visits corresponding to weeks 19, 23, 27, and 31 on the newly healed ulcer site, 5 cm away from healed ulcer site. Readings on the contralateral side will also be marked and taken and recorded. **5 recordings for each site will be taken and the average will be documented.

NOTE: if ulceration remains open after the 12th week of application – then will switch back to standard of care and the subject will be followed monthly until completion of the study.

Blood samples will be taken on each subject on weeks 4, 8 and 12 to determine serum Timolol level. We do not anticipate blood levels in our patients to be higher than those seen in patients who receive Timoptic XE® gel for ocular indication (normal range: 0.3-0.5 ng/ml). We will terminate study on patients in whom Timolol level is 0.7 ng/ml or higher.

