4.3.6 Follow-Up Phase (Visits 16 to 19/Weeks 19, 23, 27 & 31)

- The ulcer will be assessed – visual inspection – complete ulcer characteristics form (see appendix). Determine if reaches 100% epithelialization by clinician.
- Digital imaging of ulcer location, if remains non-healing then 2 images to be obtained prior to and after surgical debridement.
- Surgical debridement of ulcer if not healed, will be performed using curette or blade and standard therapy.
- Changes in concomitant medications, adverse events, compliance to offloading, will be recorded.
- Vapometer recordings will be collected on visits corresponding to weeks 19, 23, 27, and 31 ,on the ipsilateral healed ulcer site, 5 cm away from healed ulcer site. Readings on the contralateral side will also be marked and taken and recorded. **5 recordings for each site will be taken and the average will be documented

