6. STATISTICAL DESIGN

Measures:

Measures will be collected at baseline, weekly thereafter, with primary endpoint of complete healing at Visit 14/Week 14, and final secondary endpoint measurement at Visit 17/Week 31. The ulcer will be assessed weekly and will be treated as described above. A designated inter-observer (blinded to the treatment of the subjects) will regularly review images and physical exam findings to determine primary and secondary endpoints. The following measurements will be taken: size (surface area calculation), photos (digital includes ruler) and complete foot ulcer assessment (description of ulcer/characteristics), before and after debridement. Subjects where ulceration healed earlier than Visit 14/Week 14 will have follow-up assessment one week after healing, a 2nd assessment a week after, then 4 monthly visits at Weeks 19, 23, 27 & 31. If the ulceration healed after 12 weeks, then the subjects will be similarly assessed. The subject with healed ulcer will also return for follow-up visits Weeks 19, 23, 27 & 31 (visits 16, 17, 18 and 19).

During the study, if ulceration appears to be infected as determined by clinical presentation characterized by the presence of two or more signs of inflammation, the clinician will follow the protocol of obtaining wound culture for microbiology, radiographs, blood work (CBC, chemistry panel, sedimentation rate, and C-reactive protein), and treatment immediately with appropriate antibiotics. Subjects with infected ulcers will be withdrawn from study and investigators will be notified. In addition, adverse events will be well documented and treated per protocol, and subjects will be withdrawn from study.

Clinical Outcomes:

- The percentage of subjects that have complete closure of ulceration by Visit 14/Week 14 and Visit 17/Week 31. Complete healing will be defined as full re-epithelialization with no drainage, or callus formation and remains closed after 1 week of wound closure.

- Rate of wound healing to achieve complete closure. Weekly measurements of surface area will be recorded using Silhouette Mobile™ ulcer tracing and surface area calculation.
- A diabetic foot ulcer assessment form will be filled out at weekly follow-up visits, that describes characteristics of ulceration including peri-ulcer erythema, wound margins, fibrin, granular tissue, peri-ulcer pruritus, edema and location, pain, amount of drainage and type, amount of epithelialization, pain level, depth, and bioburden.

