Additional secondary analyses to evaluate the association of specific wound characteristics (such as wound size, wound location) and subject characteristics (body mass index, chronicity of the wound, history of DVT, length of diabetes, HbA1c, and ABI/toe pressure will be conducted using logistic regression. Further logistic regression will be used to investigate the relationship between the occurrence of each type of adverse event and treatment in order to adjust for each of the potential confounding factors previously listed. A two-way ANOVA with a post hoc test will be used to determine the relationship between timolol serum levels and wound healing. For demographic and clinical characteristic data at baseline, continuous variables will be summarized (when appropriate) by using mean, median, standard deviation, co-efficient of variation, minimum value and maximum value. Categorical variables will be summarized with frequency tables. Baseline comparability between the two treatment groups will be assessed by using the independent two-sample t-test or Wilcoxon rank-sum test and the Chi-square test or Fisher's exact test. Finally, we will use ANCOVA to analyze the quality of life (QOL) using the VR-36 Health Survey and the Lower Extremity Functional Scale Outcome Questionnaire, and the Charlson Comorbidity Index.

Timeline and Milestones:

7. APPENDIX 1 – Wound Scoring System

Ulcer Characteristic Form

Size: Dimensions _____ x _____ x _____ cm

Number of leg ulcers: Right Leg _____ Left Leg _____

If multiple ulcers, write distance from the study ulcer to other ulcers: _____ cm

Where is the study ulcer located? Right Leg Left Leg

Describe the study ulcer location: foot ankle low calf high calf other:

Describe the study ulcer position: dorsal ventral medial anterior lateral
 posterior

How old is the current target diabetic foot ulcer (in weeks): _____ weeks

Event that precipitated target ulcer: Ill-fitting shoes Poor foot care Acute accidental event (trauma) Not determined Other, please specify: _____

Has the study ulcer ever healed and recurred? Yes No

Has the subject ever suffered a DVT in the study limb? Yes No

Does the Study Limb/Leg Ulcer present with any of the following? (Check all that apply)

Hyperpigmentation Varicosities Dermatitis Swelling/Edema
 Lipodermatosclerosis Other: _____

	Parameter	Assessment	Score	Total
1	Erythema	Absent	0	
		Mild	1	
		Moderate	2	
		Severe	3	
2	Induration	Absent	0	
		Mild	1	
		Moderate	2	
		Severe	3	

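### Adverse events are compared only as occurrence by arm, with no event window and no account of time on drug, although application stops when the ulcer heals

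*Combined protocol and SAP*

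**What the plan says.** The between-arm model for adverse events is in Section 6 (Analyses), repeated in the Protocol Summary under Data Analysis: "Further logistic regression will be used to investigate the relationship between the occurrence of each type of adverse event and treatment", adjusted for the listed wound and subject characteristics. Neither place gives an event window, a person-time denominator or a time-to-event method.

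Section 4.3.3 ties application to closure: "Up to 12 weeks of daily applications will be done to wound until healed". The Protocol Summary, under Duration of Administration, has "Daily application for 12 weeks (starting at Visit 3/Week 3" and does not mention healing.

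On visits after early closure, Section 4.3.3 says "If ulcers heal sooner than 12 weeks, the subject will be assessed the following week for a confirmatory visit", and Section 6 (Measures) continues with "a 2nd assessment a week after, then 4 monthly visits at Weeks 19, 23, 27 & 31". Event recording goes on at those later visits; Section 4.3.6 has "Changes in concomitant medications, adverse events, compliance to offloading, will be recorded". Section 5 asks for every event in the trial to be documented.

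**The concern.** The trial is built on the expectation that timolol closes more ulcers. If it does, and application ends at closure, the timolol arm spends fewer weeks on product. An occurrence model then estimates risk per randomised patient. The listed safety outcome concerns events linked to use of the drug, and for that a reader also wants risk per week of use. The plan gives no estimate of it.

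The missing window matters as well. An on-drug count and a count to Week 31 can give different answers, and nothing fixes the choice before the data are seen.

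Ascertainment may also differ. A subject healed at Week 6 would be seen at Weeks 7 and 8 and next at Week 19, a gap of 11 weeks. An unhealed subject is seen weekly to Week 14.

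**Working it through.** **Inputs from the documents.** Closure by 12 weeks is 63% on timolol and 20% on control, with 24 per arm (Section 6, Sample Size Estimation). Application lasts at most 12 weeks. Randomisation is at Week 3 and the last visit at Week 31, so the planned window is 31 − 3 = 28 weeks.

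**Assumptions not in the documents.** Closure timing; a background event rate *a* of 2%, 5% or 10% per week that continues off drug; and a true on-drug rate ratio *r* of 1.41, chosen to equal the exposure ratio in step 1.

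**The plan's own figure.** The documents state no adverse-event rate or exposure. The closure rates come from the sample-size paragraph, and that figure reproduces: exact enumeration of the two-sided Fisher test gives 82.5% power at 24 per arm and 79.5% at 23.

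**Step 1: time on drug.**
- Constant hazard *h* = −ln(1 − p)/12, which is 0.0829 (timolol) and 0.0186 (control) per week. Mean weeks = p/h = 7.60 and 10.76; ratio 1.41.
- Linear closure over 12 weeks (closers average week 6): 0.63×6 + 0.37×12 = 8.22; 0.20×6 + 0.80×12 = 10.80; ratio 1.31.
- No closure before week 4, then linear (closers average week 8): 9.48 and 11.20; ratio 1.18.
- If closers average week 4 or week 10, the ratio is 1.49 or 1.08.

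**Step 2: all events to Week 31, constant closure hazards.** With *t* the time on drug, occurrence = 1 − E[exp(−a·r·t − a(28 − t))].
- Equal weekly rates: both arms give 1 − exp(−28a), so the risk ratio is 1.00.
- a = 2%, r = 1.41: 46.3% v 42.9%, risk ratio 1.08. With a full 12 weeks on drug, timolol would be 1 − exp(−0.02×1.41×12 − 0.02×16) = 48.2%, risk ratio 1.12. Part of the dilution is therefore due to off-drug weeks common to both arms and to the yes/no scale. Early stopping takes it from 1.12 to 1.08.
- a = 5%, r = 1.41: 78.8% v 75.3%, risk ratio 1.05.
- Counting all events in the 12 weeks after randomisation instead: 1.22 at 2% and 1.17 at 5%.

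**Step 3: on-drug events only.** With constant hazards, occurrence = a/(a + h) × (1 − exp(−12(a + h))), with *a* multiplied by 1.41 on timolol.

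| Control rate per week | Control | Timolol | Risk ratio, constant hazard | Linear | Linear from week 4 |
|---|---|---|---|---|---|
| 2% | 19.2% | 18.7% | 0.97 | 1.05 | 1.16 |
| 5% | 40.9% | 38.7% | 0.95 | 1.01 | 1.12 |
| 10% | 64.0% | 58.7% | 0.92 | 0.98 | 1.08 |

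The two percentage columns are for the constant hazard. With equal weekly rates of 1% to 10%, the constant-hazard risk ratio would be 0.71 to 0.76.

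**Step 4: what a rate could show with 24 per arm.** At a = 2% and r = 1.41, expected on-drug events are 24×10.76×0.02 = 5.2 on control and 24×7.60×0.02×1.41 = 5.1 on timolol. The standard error of the log rate ratio is √(1/5.2 + 1/5.1) = 0.62, so an approximate 95% interval around 1.41 runs from 0.42 to 4.8. At a = 5% there are 12.9 events in each arm and the interval is 0.65 to 3.05. Power is about 8% to 14% over these rates.

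**The case against.** A reader might infer that the planned analysis is biased in timolol's favour, or that a clear excess would look like no difference. The documents do not support that. It needs a count restricted to on-drug events, which the plan nowhere specifies; recording runs to Week 31 in both arms. Over that span equal rates give a risk ratio of 1.00, and a true excess is diluted but keeps its direction. Even with an on-drug count, the excess stays visible if closures start at week 4.

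Nor do weekly visits stop at healing. Two weekly checks follow. Section 6 also has transepidermal water loss measured weekly after closure, so the visit pattern between those checks and Week 19 is not settled. The ascertainment gap is possible, not established.

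Risk per randomised patient over equal planned follow-up is a legitimate target, because shorter treatment is itself a result of healing. A rate per week on drug conditions on something that happens after randomisation: on-drug weeks come increasingly from non-healers, in different proportions by arm. Adverse events are the third secondary safety outcome, Section 6 also reports numbers of events, and precision is poor under either analysis.

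All of this stands. It argues against replacing the occurrence comparison. It does not supply the missing window or an estimate of risk per week of use.

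**Conclusion.** The point holds as a gap in the safety analysis. The plan gives occurrence by arm with no window and no measure of exposure, while its own closure rates imply about 29% less time on drug for timolol under constant hazards (1 − 7.60/10.76). Across the closure timings tried, the exposure ratio runs from 1.08 to 1.49. Counted to Week 31, an on-drug rate ratio of 1.41 shows as about 1.05 to 1.08. Counted on drug only, it could show as anything from 0.92 to 1.16.

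These sizes rest on the planned 63% v 20%, the assumed closure timing and background rates, and completed follow-up. Section 6 withdraws subjects with adverse events, so equal calendar follow-up is a plan rather than a certainty. They also rest on application ending at healing. If application ran the full 12 weeks regardless, time on drug would not differ for this reason and only the missing window would remain. The primary efficacy test is unaffected; this is an inexpensive improvement to a secondary safety outcome.

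**What to change.** In Section 6 (Analyses) and the matching Protocol Summary text:
- Keep the occurrence comparison by randomised arm and state the period it covers.
- Beside it, pre-specify the adverse-event rate per on-drug patient-week by arm, with an exact rate ratio and confidence interval.
- Use one window for both arms: first application to last application plus a fixed lag (for example 7 days), with events and patient-weeks counted over the same window. State whether first events or all events are counted.
- Tabulate post-treatment events separately.
- Record the date of last application for every subject.
- Reconcile the Protocol Summary and Section 4.3.3 on duration of application, because the denominator depends on it.

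The cost is plan wording and one date per subject, settled before unblinding. The downsides should be stated in the plan: the rate assumes a roughly constant hazard, it conditions on post-randomisation exposure, and with 24 per arm it should be read as an estimate and not as a powered test.

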5. ADVERSE EVENTS

All adverse events reported spontaneously by the subject/or in response to questioning or observation by the investigator will be recorded.

Reporting of Adverse Events:

The Investigator will be responsible for assessing the relationship of the adverse event to the investigational product, and the seriousness and expectedness of the adverse event at the time of occurrence. All adverse events that occur during the trial will be documented.

AE's/SAE's reported during the study, or SAE's reported within 30 days of the end of the study, should be followed to resolution of the AE/SAE or, within thirty days from the end of the study, a further and final assessment of the outcome should be made. Each AE will be categorized as "serious" or "not serious" based on the definition of an SAE. An SAE is defined as an AE resulting in at least one of the outcomes described in the sections below.

The severity of AEs will be classified as "mild", "moderate", or "severe", based on the following definitions:

- Mild: Awareness of sign, symptom, or event, but easily tolerated; does not interfere with usual daily activities or tasks.
- Moderate: Discomfort enough to cause interference with usual daily activity; may warrant therapeutic intervention.
- Severe: Incapacitating; inability to perform usual activities and daily tasks; significantly affects clinical status; requires therapeutic intervention.

Adverse events will be assigned a relationship (causality) to the study products. The Investigator will be responsible for determining the relationship between an AE and the study product. The

type of event, organ system affected, and timing of onset of the event will be factors in assessing the likelihood that an AE is related to the treatment. Relationship of AEs to study products will be classified as follows:

- Not Related: No relationship exists between the AE and the treatment. The event is attributed to a pre-existing medical condition or an intercurrent event unrelated to the study product.
- Possibly Related: Follows the treatment, but may have developed as a result of an underlying clinical condition or treatments/interventions unrelated to the study product.
- Probably Related: Follows the treatment, but is unlikely to have developed as a result of the subject's underlying clinical condition or other treatment or other interventions.

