- Number of incident subjects with infection, osteomyelitis and acute Charcot during the study, will be withdrawn from the study.
- Number of incidences of adverse effects will be reported from all sites and will be withdrawn from the study.
- VR-36 Health Survey, and the Lower Extremity Functional Scale Outcome Questionnaire (self-administered questionnaires) will be used to measure quality of life and provided at beginning of the study and at the study endpoint.
- Rate of transepidermal water loss will be measured weekly subsequent to wound closure and compared in the two groups.

Sample Size Estimation:

From previous studies, we expect that about 20% of the study subjects will heal in the control arm of our study by the 12th week of care. We estimate that the experimental treatment will improve this outcome with 63% of the study subjects healing by the 12th week of care (a healing rate close to that reported in the most recent case series of topical use of timolol on chronic wounds).

We will perform simple allocation of the subjects using an electronic randomization for treatment assignment-since our target enrollment population is fairly homogenous.

The sample size calculation will require the enrollment of 48 subjects (24 subjects in each arm) to provide a power of 80% to detect a difference of 43% (= 63% - 20%) in the rate of ulcer healing between the two arms by using two-sided Fisher's exact test at a significance level of 5%. It is estimated that the overall attrition will be 35%. Specifically, 10% of the subjects who are enrolled will be exited from the study prior to randomization, 10% will not meet the primary endpoint analysis inclusion requirement and 15% will not complete the study due to other factors such as treatment failure, loss to follow-up, adverse events, clinical/safety issues, and/or non-compliance. We will track the various reasons for study exit. Therefore, 138 subjects (69 subjects in each arm) will be recruited into the study after taking into account the overall attrition of 35%.

The consulting statistician will review implementation and compare major baseline demographic and prognostic characteristics to ascertain that randomization was successful. The power analysis was formulated using the STPLAN Version 4.5 (2010) with the input of the study consultant biostatistician.

Analyses:

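### The only between-arm adverse-event analysis is a logistic regression per event type adjusted for eight factors in 48 subjects, so event types seen in only a few subjects will usually have no usable adjusted estimate

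*Combined protocol and SAP*

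**What the plan says.** Section 6, Analyses (repeated under Data Analysis in the Protocol Summary) first plans a logistic regression to study the association of wound and subject characteristics. The factors are ulcer size, ulcer location, BMI, ulcer duration, previous DVT, duration of diabetes, HbA1c and ABI or toe pressure. The wound characteristics are given as examples, so the list is open-ended. The sentence names neither an outcome nor a treatment term.

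The next sentence concerns safety: "Further logistic regression will be used to investigate the relationship between the occurrence of each type of adverse event and treatment", and this is done "in order to adjust for each of the potential confounding factors previously listed". No minimum event count, limit on covariates, or exact or penalised method is given.

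Elsewhere, the Protocol Summary lists as a secondary safety outcome "Adverse events associated with the use of timolol", while Section 5 says "All adverse events that occur during the trial will be documented". Section 6 also says that the number of adverse effects will be reported, but not expressly by arm.

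On size, Section 6 says that the calculation "will require the enrollment of 48 subjects (24 subjects in each arm) to provide a power of 80" per cent.

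**The concern.** A logistic model with treatment and eight covariates has at least nine slopes. Once events are split by type, a 48-subject trial will often have only a handful per type. Maximum likelihood then tends to fail through separation: some combination of covariates divides subjects with the event from those without it, and at least one log odds ratio runs off to infinity. Software typically prints a very large number with an enormous standard error, or a convergence warning.

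Adverse events are a named secondary safety outcome, and the plan specifies no other comparison of them between arms. For any type where the model fails, no pre-specified comparison remains, and the choice of what to report instead would be made after seeing the data.

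The association model raises a related, smaller concern. If its outcome is closure, the number of closures is also low for eight factors.

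**Working it through.** **1. The plan's own figure.** Inputs from Section 6: control closure 20%, timolol closure 63%, "two-sided Fisher's exact test at a significance level of 5" per cent. Exact enumeration of Fisher power gives 79.5% at 23 per arm and 82.5% at 24 per arm. The stated 24 per arm (48 in total) is reproduced and is used below.

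**2. Events per slope for adverse events.** Slopes = 8 factors + treatment = 9, more if location has several categories. The documents give no event rates, so these are assumed:
- 5%: 48 × 0.05 = 2.4 events, 2.4/9 = 0.27 per slope
- 10%: 48 × 0.10 = 4.8 events, 4.8/9 = 0.53 per slope
- 20%: 48 × 0.20 = 9.6 events, 9.6/9 = 1.07 per slope

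**3. How often the joint model has no finite fit.** Datasets were simulated with 24 per arm, six continuous covariates, binary location (50%), and DVT history at 10% or 30%. Events were unrelated to any covariate. Complete or quasi-complete separation was checked by linear programming, with at least 600 datasets per setting. A dataset with no events counts as non-finite. DVT prevalence and location coding are assumptions. Ranges are across repeated runs.

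| Event rate | Any coefficient non-finite, DVT 10% | Any coefficient non-finite, DVT 30% | Treatment coefficient non-finite |
|---|---|---|---|
| 5% | 92–94% | 80–84% | 69–76% |
| 10% | 69–75% | 43–46% | 26–34% |
| 15% | 51–53% | 20–23% | 8–13% |
| 20% | 38–42% | 7–10% | 2–5% |

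**4. How much is due to an empty arm.** P(no events in at least one arm) = 1 − (1 − (1 − p)^24)².
- p = 5%: 0.95^24 = 0.292; 1 − 0.708² = 50%
- p = 10%: 0.90^24 = 0.080; 1 − 0.920² = 15%

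A model with treatment alone would fail in these cases too. The covariates account for the rest: roughly 20 of the 70 points at 5%, and 15 of the 30 at 10%.

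**5. By number of events, all factors together (any coefficient non-finite).**

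| Events among 48 | DVT 10% | DVT 30% |
|---|---|---|
| 2 | 99.5% | 98% |
| 3 | 96% | 80% |
| 4 | 81% | 53% |
| 5 | 67% | 31% |
| 6 | 57% | 21% |
| 10 | 33% | 4% |

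Binary location is lenient: the ulcer form in Appendix 1 offers five locations and six positions. With four location categories and DVT at 10%, failure is 87% at 6 events and 54% at 10.

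**6. One factor at a time.**

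| Events among 48 | Treatment alone, 2·C(24,k)/C(48,k) | Treatment + one continuous factor | Treatment + DVT (10%) |
|---|---|---|---|
| 2 | 49% | 51% | 90% |
| 3 | 23% | 21% | 78% |
| 4 | 11% | 11% | 70% |

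A single continuous factor adds almost nothing to the failure rate of treatment alone. DVT history does.

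**7. A larger analysed number.** Section 6 also speaks of recruiting 138 with 35% attrition. If 138 × 0.65 ≈ 90 were analysed (DVT 10%), the joint model would still have a non-finite coefficient in 74%, 45% and 18% of fits at event rates of 5%, 10% and 20%.

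**8. The association model, if the outcome is closure.** Expected closures = 24 × 0.20 + 24 × 0.63 = 4.8 + 15.1 = 19.9. Per slope: 19.9/8 = 2.5, or 19.9/9 = 2.2 if treatment is added. With treatment included, fits are non-finite in 17% (DVT 10%) or 1% (DVT 30%), so the main problem is overfitting.

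**The case against.** **The failure rates depend on figures that the plan does not give.** This stands. A reader might infer that most adverse-event models will fail. For a type at 20%, failure is below half even with DVT at 10%, and about 7–10% with DVT at 30%. The statement holds for sparse types only.

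**The text does not say that the factors enter jointly.** This also stands: adjusting for each factor could mean one at a time, and then the problem shrinks to DVT history and very rare types. That reading leaves eight adjusted odds ratios per event type with none named as the main one.

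**The safety comparison is not lost.** A reader might infer that it is. Often only the DVT or location coefficient is infinite, and part of the failure in the treatment coefficient comes from an empty arm, which no choice of covariates cures. Events are also all recorded, so a table by arm can still be made; it is just not pre-specified.

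**Adjustment is legitimate in a small trial with simple allocation.** Agreed. Under randomisation, baseline differences arise by chance, so confounding is a loose term, but adjusting for prognostic factors is not wrong. The number of factors is the difficulty.

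**Two further inferences go too far.** One is that the closure model will inflate the treatment odds ratio: the sentence states no treatment term, and treatment is compared on closure by the Fisher and log-rank tests. The other is that timolol-associated events have no meaning in the placebo arm: Section 5 has the investigator judge relationship to the study products, and the trial is double blinded, so attribution can be made in both arms. The planned model uses occurrence, not attribution.

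**Conclusion.** The point holds in a conditional form. The plan's only between-arm adverse-event analysis is unsuited to sparse event types at 48 subjects, and nothing in the plan says what to do when a model fails. With joint entry, types seen in up to about 4 subjects have at least one non-finite coefficient in more than half of fits under both DVT assumptions; this extends to about 7 subjects if DVT prevalence is 10%. For common types the model can usually be fitted, though with few events per slope. These figures assume joint entry, binary location, DVT prevalence of 10–30% and events unrelated to the covariates.

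The association model needs an outcome. If that is closure, it is overfitted rather than impossible to fit. These are secondary and safety analyses, and the primary comparison of closure does not depend on them.

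**What to change.** **Adverse events.** Replace the adjusted models in Section 6 and the Protocol Summary with a comparison by arm of all treatment-emergent adverse events, regardless of attributed relationship. For each type, give the number and percentage of subjects per arm, the risk difference and its exact 95% confidence interval, with no covariate adjustment. Align the Protocol Summary's secondary safety outcome with this. Events judged related can be tabulated separately.

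**Association model.** Name the outcome and say whether treatment is included. If the outcome is closure, either limit the model to a few pre-specified factors fitted by Firth-penalised logistic regression, or examine the factors one at a time and label the results exploratory.

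**Cost.** Wording only, with no new data and no change to sample size or the primary test. The small loss is that adjusted odds ratios for adverse events are no longer reported. The exact intervals will be wide, which is a fair reflection of 24 subjects per arm.
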